6.5 Concomitant Therapy

Record in the eCRF all concomitant therapies (e.g., medicines or nondrug interventions) used from the time the participant signs the Prescreening informed consent until completion of the study, including any changes. For prescription and over-the-counter medicines, vaccines, vitamins, and herbal supplements, record the name, reason for use, dates administered, and dosing information.

Any additional concomitant therapy that becomes necessary during the study and any change to concomitant drugs must be recorded in the corresponding section of the eCRF, noting the name, dose, duration, and indication of each drug.

Contact the Medical Monitor for any questions on concomitant or prior therapy.

6.5.1 Permitted Medicines

The only permitted medications are the following:

1. Any medications (other than prohibited in Section 6.5.2) that are considered necessary for the participants' welfare and will not interfere with the study intervention may be given at the Investigator's discretion.
2. Other drugs to be used for non-steroid premedication when indicated (e.g., antihistamine and acetaminophen; steroids are not allowed to be used for premedication).
3. Other drugs, including steroids, as indicated, may be used for the treatment of anaphylactic reactions, IRRs, and severe hypersensitivity reactions/flu-like symptoms and irAEs (see Section 6.9).
4. Blood transfusions and erythroid growth factors are permitted as clinically indicated.

Any medicines that are considered necessary to protect the participant's welfare in emergencies may be given at the Investigator's discretion, regardless if it results in a protocol deviation.

6.5.2

Prohibited Medicines

The following treatments must not be administered during the 28-day Screening period and for the duration of study intervention. If the administration of a nonpermitted concomitant drug becomes necessary during the study, the participant will be withdrawn from study intervention (the Sponsor may be contacted to discuss whether the study intervention must be discontinued).

- Immunotherapy, immunosuppressive drugs (e.g., chemotherapy or systemic corticosteroids), or other experimental pharmaceutical products are prohibited. Exceptions are allowed for short-term treatment of allergic reactions or for the treatment of irAEs, specifically:
 - Short-term administration of systemic steroid (i.e., for allergic reactions or the management of irAEs) is allowed.
 - Steroids with no or minimal systemic effect (topical, intranasal, intraocular, inhalation) are allowed.
 - Hormone replacement with corticosteroids for adrenal insufficiency is allowed if the steroids are administered only for the purpose of hormonal replacement and at doses ≤ 10 mg or equivalent prednisone per day.
- Prophylactic use of corticosteroids for IRRs is prohibited.
- Concomitant local or regional treatment (radio/chemo-embolization) is prohibited.
- Other systemic anticancer therapy.
- Live vaccines are prohibited. Administration of inactivated vaccines is allowed (e.g., inactivated influenza vaccines).
- Any traditional Chinese medication used as anticancer treatment (regardless of the type of cancer) is prohibited. Traditional Chinese medication for indications other than anticancer treatment, such as supportive care, may be administered at the discretion of the Investigator. List of prohibited Chinese medications is provided in the [Appendix 7](#).
- Herbal remedies with immunostimulating properties (e.g., mistletoe extract) or known to potentially interfere with major organ function (e.g., hypericin).

Medications other than those specifically excluded in this study (see above) may be administered for the management of symptoms associated with the administration of bintrafusp alfa as required. These might include analgesics, antinausea medications, antihistamines, diuretics, antianxiety medications, and medication for pain management, including narcotic agents.

6.5.3

Other Interventions

Permitted Procedures

- Palliative organ-sparing radiotherapy may be administered only for specific clinical indications during the study. The assessment of PD will be made according to RECIST 1.1 and not based on the necessity for palliative radiotherapy.

Prohibited Procedures

- Major surgery within 4 weeks before the start of the study. Discuss with the Medical Monitor if unplanned major surgery is required on study to plan for timing of re-treatment. Any diagnostic biopsies collected for clinical reasons during the study should be documented as a concomitant procedure including the outcome of available pathology reports.

6.6 Dose Selection and Modification

Participants will receive an intravenous infusion of bintrafusp alfa at a dose of 1200 mg over 1 hour (-10 minutes/+ 20 minutes, i.e., over 50 to 80 minutes) once every 2 weeks as detailed in the Schedule of Activities ([Table 1](#)).

Dose modification of bintrafusp alfa is not allowed.

6.7 Study Intervention After the End of the Study

After a participant has completed the study, has withdrawn consent, or has been withdrawn early, symptom guided appropriate treatment will be administered, if required, in accordance with the study site's standard of care and generally accepted medical practice and depending on the participant's individual medical needs. Participants will be followed for survival and AEs as specified in the Schedule of Activities ([Table 1](#)).

On withdrawal from the study, participants may receive whatever care they and their physicians agree upon.

6.8 Special Precautions

Any treatment-emergent adverse event (TEAE) that is assessed as potentially related to bintrafusp alfa, may require permanent or transient discontinuation of bintrafusp alfa treatment.

Single laboratory values out of the normal range that do not have any clinical correlation do not necessarily need treatment interruption. Questions or concerns with regard to management and/or follow-up of TEAEs should be discussed with the Medical Monitor.

Immune-related AEs, IRRs including hypersensitivity, anemia, TGF- β inhibition mediated skin reactions, and bleeding events are managed and followed up in their respective sections as indicated below. Permanent study intervention discontinuation may be recommended, so the relevant section must be reviewed:

- For suspected irAEs, general management by NCI-CTCAE v5.0 toxicity grading is listed in Section [6.9.2](#). Recommended guidance and management for specific irAEs as per published guidelines is provided in [Appendix 5](#).
- IRR and hypersensitivity reaction guidance are presented in Section [6.9.1](#).
- Anemia guidance is presented in Section [6.9.4](#).

- Potential TGF- β inhibition mediated skin AEs guidance and management are provided in Section **Error! Reference source not found..**
- Guidance and management of bleeding events are discussed in Section **6.9.5.**

General guidance:

- In any case, if ≥ 2 doses are missed due to AE, the Medical Monitor should be consulted.
- Inability to reduce corticosteroid dose to 10 mg or less of prednisone or equivalent per day within 12 weeks is an indication for permanent treatment discontinuation (except for use of steroids as hormone substitution).
- Persistent Grade 2 or 3 adverse reactions (excluding endocrinopathies controlled with hormone replacement therapy) that do not recover to Grade 0 to 1 within 12 weeks after last dose of study intervention is an indication for permanent treatment discontinuation.

In general, the following applies for TEAEs related to bintrafusp alfa that are not covered by the recommendations for irAE management in [Appendix 5](#):

Grade 4 treatment-related TEAEs

Any Grade 4 treatment-related TEAEs require permanent treatment discontinuation, except:

- Endocrinopathies that have been controlled by hormone replacement,
- Isolated laboratory values out of normal range that do not have any clinical correlation. Discuss with Medical Monitor regarding work-up, management, and treatment continuation versus hold versus discontinuation for isolated Grade 4 laboratory abnormalities
- If alternative explanation is identified for Grade 4 non-tumor bleeding.

See [Appendix 5](#) for guidance on specific Grade 4 irAEs, as most require permanent treatment discontinuation.

Grade 3 treatment-related TEAEs

1. Participants with any severe or Grade 3 treatment-related adverse reactions that recur should be permanently discontinued. Exceptions may be considered for the following after discussion with Medical Monitor:

- Transient Grade 3 flu-like symptoms or fever that is controlled with medical management
- Transient Grade 3 fatigue, local reactions, headache, nausea, emesis that resolves to \leq Grade 1 or baseline
- Tumor flare phenomenon defined as local pain, irritation, or rash localized at sites of known or suspected tumors
- Any Grade ≥ 3 drug-related amylase or lipase abnormality that is not associated with symptoms or clinical manifestations of pancreatitis

- Grade 3 Hgb decrease (< 8.0 g/dL) that is clinically manageable with blood transfusions or erythroid growth factor use
- Increases in ECOG PS ≥ 3 that resolves to ≤ 2 by Day 1 of the next infusion (i.e., infusions should not be given if the ECOG PS is ≥ 3 on the day of treatment and should be delayed until ECOG PS ≤ 2)
- KA and cutaneous squamous cell carcinoma (cSCC)
- Grade 3 non-tumor bleeding requiring intervention or hospitalization if alternative explanation can be identified (such as concomitant use of antithrombotic agents, traumatic event, etc).

2. See [Appendix 5](#) for guidance on specific Grade 3 irAEs as many require permanent treatment discontinuation, including pneumonitis and nephritis.
 - AST or ALT > 5 times ULN or total bilirubin > 3 times ULN must be permanently discontinued, except for participants with liver metastases (e.g., who begin treatment with Grade 2 AST or ALT). These participants should be discontinued if AST or ALT increases by $\geq 50\%$ relative to baseline and lasts for at least 1 week.
3. Persistent Grade 3 adverse reactions (excluding endocrinopathies controlled with hormone replacement therapy) that do not recover to Grade 0 to 1 within 12 weeks after last dose of treatment.

Grade 2 treatment-related TEAEs

1. If a Grade 2 treatment-related TEAE resolves to Grade ≤ 1 by the day before the next infusion, study intervention may be continued.
2. If a Grade 2 treatment-related TEAE does not resolve to Grade ≤ 1 by the day before the next infusion, but it is manageable and/or not clinically relevant, the Medical Monitor should be consulted to assess if it is clinically reasonable to administer the following infusion.

Note that treatment recommendations regarding continuation, hold, or discontinuation by grade are different depending on the specific toxicity (see [Appendix 5](#)). Toxicity grading is assigned based on NCI-CTCAE v5.0.

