4. Availability of either archival tumor tissue or fresh core or excisional biopsy of a tumor lesion (primary or metastatic, excluding bone biopsies) is mandatory to determine HMGA2 expression level prior to enrollment. Fine needle aspirates are not acceptable. Tumor material must be suitable for biomarker assessment as described in the Laboratory Manual. If an archival sample is submitted during Prescreening for HMGA2 testing, a fresh tumor biopsy during the Screening period is additionally encouraged if feasible for exploratory biomarker analysis.
5. HMGA2 high tumor expression is required. If a tumor specimen is assessed as not evaluable for HMGA2 expression by the central laboratory, another sample may be submitted to assess for HMGA2 high status. The status of tumor HMGA2 expression (high versus not high) will be determined by a centralized RT-PCR assay with predefined cutoff

(documented in the applicable documentation submitted to the Food and Drug Administration [FDA]) and with appropriate regulatory status.

6. Have Eastern Cooperative Oncology Group (ECOG) PS of 0 to 1 at study entry and Day 1 of treatment with bintrafusp alfa.
7. Life expectancy \geq 12 weeks as judged by the Investigator at study start.
8. Have adequate organ function:
 - a. Adequate hematological function defined by absolute neutrophil count $\geq 1.5 \times 10^9/L$, platelet count $\geq 100 \times 10^9/L$, and hemoglobin (Hgb) $\geq 9 \text{ g/dL}$.
 - b. Adequate hepatic function defined by a total bilirubin level \leq the upper limit of normal (ULN), aspartate aminotransferase (AST) and alanine aminotransferase (ALT) levels $\leq 1.5 \times \text{ULN}$. For participants with liver involvement in their tumor, AST $\leq 5.0 \times \text{ULN}$, ALT $\leq 5.0 \times \text{ULN}$, and bilirubin $\leq 3.0 \times \text{ULN}$ are acceptable.
 - c. Adequate renal function defined by creatinine $\leq 1.5 \times \text{ULN}$ or calculated creatinine clearance (CrCL) $\geq 30 \text{ mL/min}$ for participant with creatinine $> 1.5 \times \text{ULN}$ (glomerular filtration rate can also be used).

Note: CrCL should be calculated per institutional standard. If no local guideline is available, CrCL should be calculated using the Cockcroft-Gault Method:

$$\text{CrCL} = ([140-\text{age}] \times \text{weight [kg]} \times [0.85 \text{ for females only}]) / (72 \times \text{creatinine}).$$

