2.2 Hepatitis	
Definition: A disorder characterized by a viral pathologic process involving the liver parenchyma Diagnostic work-up Monitor patient for abnormal liver blood tests: AST, ALT, and bilirubin prior to each infusion and/or weekly if G1 liver function test elevations. No treatment is recommended for G1 liver function test abnormality For G2 or higher: Work-up for other causes of elevated liver enzymes should be tested, viral hepatitis, alcohol history, iron study, thromboembolic event, liver ultrasound, cross-sectional imaging for potential liver metastasis from primary malignancy. If suspicion for primary autoimmune hepatitis is high, can consider ANAs, antismooth muscle antibodies, antineutrophil cytoplasmic antibodies. If patients with elevated alkaline phosphatase alone, g-glutamyl transferase should be tested. For isolated elevation of transaminases, consider checking CK for other etiologies	
Grading	Management
All patients	Counsel all patients to be aware of and inform their health care provider immediately if they experience: Yellowing of skin or whites of the eyes Severe nausea or vomiting Pain on the right side of the abdomen Drowsiness Dark urine (tea colored) Bleeding or bruising more easily than normal Feeling less hungry than usual
G1: Asymptomatic (AST or ALT > ULN to 3.0 x ULN and/or total bilirubin > ULN to 1.5 x ULN)	Continue ICPi with close monitoring; consider alternate etiologies Monitor laboratories one to two times weekly Manage with supportive care for symptom control
G2: Asymptomatic (AST or ALT > 3.0 to \leq 5 x ULN and/or total bilirubin > 1.5 to \leq 3 x ULN)	Hold ICPi temporarily and resume if recover to G1 or less on prednisone \leq 10 mg/d For Grade 2 hepatic toxicity with symptoms, may administer corticosteroid 0.5-1 mg/kg/d prednisone or equivalent if the abnormal elevation persists with significant clinical symptoms in 3-5 days Increase frequency of monitoring to every 3 days Infliximab might not be the most appropriate treatment option in the situation of immune-mediated hepatitis given the potential risk of idiosyncratic liver failure (Note: No clear evidence shows the liver toxicity from infliximab from other studies) In follow-up, may resume ICPi treatment followed by taper only when symptoms improve to G1 or less and corticosteroid \leq 10 mg/d; taper over at least 1 month Patients should be advised to stop unnecessary medications and any known hepatotoxic drugs

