G3: Symptomatic liver dysfunction, fibrosis by biopsy, compensated cirrhosis, reactivation of chronic hepatitis (AST or ALT 5-20 x ULN and/or total bilirubin 3-10x3 ULN)	Permanently discontinue ICPi Immediately start corticosteroid 1-2 mg/kg methylprednisolone or equivalent If corticosteroid refractory or no improvement after 3 days, consider mycophenolate mofetil or azathioprine (if using azathioprine should test for thiopurine methyltransferase deficiency) Laboratories at daily or every other day; consider inpatient monitoring for patients with AST/ALT > 8 x ULN and/or elevated TB 3 x ULN

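### Section 6.8 and the Appendix 5 hepatitis table contradict each other on stopping treatment for some liver test rises in participants with liver metastases

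*Protocol*

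**What the plan says.** Four places in the protocol bear on this.

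- **Section 5.1, criterion 8b.** There is a separate, wider limit that begins "For participants with liver involvement in their tumor, AST". It accepts AST and ALT up to 5.0 x ULN and bilirubin up to 3.0 x ULN.
- **Section 6.8, Grade 3 treatment-related TEAEs, item 2.** Participants with AST or ALT above 5 x ULN, or total bilirubin above 3 x ULN, "must be permanently discontinued, except for participants with liver metastases (e.g., who begin treatment with Grade 2 AST or ALT"). The replacement rule is "These participants should be discontinued if AST or ALT increases by" at least 50% "relative to baseline and lasts for at least 1 week". It contains no bilirubin criterion.
- **Appendix 5, Table A2, section 2.2 (Hepatitis).** Grade 1 (AST or ALT up to 3.0 x ULN) continues treatment. Grade 2 (above 3.0 to 5 x ULN, or bilirubin above 1.5 to 3 x ULN) has the instruction "Hold ICPi temporarily and resume if recover to G1 or less on prednisone" 10 mg/d or less. Grade 3 includes "reactivation of chronic hepatitis (AST or ALT 5-20 x ULN and/or total bilirubin 3-10x3 ULN" and calls for permanent discontinuation. No row mentions liver metastases or adjusts for baseline.
- **Section 6.8, scope sentence.** It says that the rules that follow are, as a generality, for related events that the irAE guidance in Appendix 5 does not deal with.

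**The concern.** The trial deliberately enrols participants with liver involvement and raised liver tests. For some rises in this group, one part of the protocol lets treatment go on and another ends it permanently. Two sites could both follow the protocol and treat the same participant in opposite ways. What is at stake is a permanent discontinuation instruction, and the safety monitoring behind it, in a group whose liver tests are already abnormal at entry. The recorded reasons for discontinuation and the exposure data would then partly reflect which page the site consulted.

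**Working it through.** The plan states no figure on this point, so there is none to reproduce. The check applies both rules to the same values. Write *b* for baseline and *x* for the on-treatment value of AST or ALT, both in multiples of ULN.

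**Inputs**
- 6.8 exception: discontinue if *x* ≥ 1.5*b* for at least 1 week.
- Table A2: continue at *x* ≤ 3; hold at 3 < *x* ≤ 5; permanent stop at *x* > 5.
- Criterion 8b: *b* may be as high as 5.0.

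**Where 6.8 does not stop and Table A2 stops for good.** This needs 5 < *x* < 1.5*b*, which is possible only if *b* > 5/1.5 = 3.33.

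| Baseline *b* | 1.5*b* | Range of *x* in conflict |
|---|---|---|
| 3.5 | 5.25 | 5 to 5.25 |
| 4.0 | 6.0 | 5 to 6.0 |
| 4.5 | 6.75 | 5 to 6.75 |
| 5.0 (8b ceiling) | 7.5 | 5 to 7.5 |

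Example: 4.5 to 6.0 x ULN. 6.0/4.5 = 1.33, a rise of 33%, which is below the 50% threshold. The exception does not stop treatment; Table A2 Grade 3 stops it permanently.

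**Where the two agree.** At 4.0 to 6.0 x ULN, 6.0/4.0 = 1.50. If this lasts a week, both texts stop treatment.

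**Where the answer depends on how the exception is read.** The Grade 2 baseline is introduced only as an example, so the exception can be read as covering every participant with liver metastases.
- On that reading, for *b* ≤ 3/1.5 = 2.0 a 50% rise can end at 3 x ULN or less. From 1.0 to 1.5 x ULN, 6.8 would discontinue and Table A2 Grade 1 would continue.
- For *b* between 2.0 and 3.33 the difference is milder. From 3.0 to 4.5 x ULN, 6.8 discontinues and Table A2 holds with possible resumption.
- If the exception is confined to Grade 2 baselines (above 3 to 5 x ULN), the 50% rule starts above 1.5 × 3 = 4.5 x ULN. The low-baseline cases then fall away. The conflict in the table above and the bilirubin gap remain.

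**Bilirubin.** The exception removes both limits, AST/ALT above 5 x ULN and bilirubin above 3 x ULN, and replaces only the first. A participant whose bilirubin rises from 1 to 8 x ULN with stable AST and ALT meets no criterion in the exception, but falls in Table A2 Grade 3 and would be stopped permanently.

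**The case against.** The strongest reply is precedence. The scope sentence reserves 6.8 for events outside the Appendix 5 guidance, and 6.8 closes by noting that hold and stop advice differs by toxicity and pointing to Appendix 5. On that view Table A2 governs hepatitis and nothing conflicts. This is a defensible route, but the text does not secure it. The sentence is qualified as a generality. The liver rule is placed under the item on Grade 3 irAEs that refers to Appendix 5, and its cut-offs of 5 and 3 x ULN are the lower bounds of the Table A2 Grade 3 row. It therefore addresses the same event. If Appendix 5 prevails, the exception has no effect for immune-related hepatitis; if 6.8 prevails, Table A2 contradicts it. Nothing says which governs while the cause of a raised value is still being worked up.

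Other parts of the opposing case do stand, and they rule out stronger readings that a reader might infer.

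- *That 6.8 plainly requires discontinuation for a 50% rise within the normal range* (for example 0.5 to 0.8 x ULN, +60%). The rule sits under a Grade 3 heading and can be read as applying only to participants excepted from the 5 x ULN stop. The text is ambiguous; it does not clearly say this.
- *That a participant admitted at 4.0 x ULN who reaches 4.6 (+15%) must be held and then stopped under the 12-week non-recovery rule.* That chain needs a new treatment-related or immune-related reaction. Appendix 4 excludes conditions present at entry that do not worsen, and 6.8 sends unresolved but manageable Grade 2 related events to the Medical Monitor.
- *That bilirubin rises have no rule at all.* The Table A2 bilirubin rows remain, as do the general 6.8 rules on recurrent or persistent Grade 3 and on Grade 4 related events. The gap is confined to the exception.
- *That the planned liver-metastasis subgroup results are at risk.* The SAP 8.2 subgroups are optional and exploratory, and SAP 4.1 says that no efficacy analyses will be done after the early discontinuation of the study.

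**Conclusion.** The contradiction is real and the text is wrong as written. It has three parts:

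1. For a related AST or ALT rise from a baseline above 3.33 x ULN to a value above 5 x ULN but below 1.5 times baseline, the 6.8 exception and Table A2 Grade 3 give opposite instructions. The range is widest, 5 to 7.5 x ULN, at the highest baseline that 8b allows.
2. The exception lifts the bilirubin limit with no replacement, while Table A2 still stops permanently from 3 x ULN.
3. It is unclear whether the 50% rule reaches participants with normal or Grade 1 baselines.

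Parts 1 and 2 hold on either reading of the baseline example. Part 3 is an ambiguity, not a demonstrated conflict. All of this assumes that the rise is judged treatment-related or immune-related.

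The number of participants affected cannot be derived. The documents give no rate of liver metastases. Assuming 20% to 40% of 29 would give 5.8 to 11.6 people, but that counts everyone with liver involvement, not those whose values fall in the conflict range. The point does not touch the sample size or power, and no effect on the efficacy analyses is claimed.

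**What to change.** Reconcile 6.8, Grade 3 item 2, with Appendix 5, Table A2, section 2.2, so that one stated rule governs AST/ALT and bilirubin elevations in participants with liver metastases. Both places should say:

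- whether the exception applies to the Table A2 hold and permanent-stop rows;
- which baseline values it covers;
- which text governs bilirubin in this group;
- which text takes precedence when the cause is not yet established.

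The clinical content is for the sponsor to decide; this review takes no position on which rule is right. The cost is amendment wording in two places, with no new assessments and no additional participants.
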